Quantitative observational comparative effectiveness of quadratus lumborum block with liposomal bupivacaine (Exparel®) versus thoracic epidural analgesia in patients undergoing laparoscopic colectomy

NCT03827291

Document Date: 09/27/2022

Purpose of the Study

We believe that a quadratus lumborum block with liposomal bupivacaine(Exparel®) or a quadratus lumborum block with an admixture of bupivacaine will provide roughly equivalent analgesia and opioid use when compared with postoperative analgesia in a historical cohort that received thoracic epidural analgesia. We believe participants who receive the quadratus lumborum block will result in improved early mobilization, fewer complications such as block failure, urinary retention, and pruritis, and decreased overall pharmacy costs compared to the patients who received thoracic epidural analgesia.

Background & Significance

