Laparoscopic colectomy is a surgical procedure that is primarily performed for resection of a GI malignancy. While most of the procedure is performed via laparoscopic ports in the anterior abdominal wall, the resected specimen is typically delivered through a small lower abdominal laparotomy, which results in a moderately severe burden of pain for these patients. Enhanced recovery after surgery (ERAS) protocols are aimed at improved return to function with minimal disruption in the functional capacity, and have been shown to reduce hospital length of stay, complications, and costs. One standard therapeutic component of the ERAS program at Duke for colorectal surgery is thoracic epidural analgesia (TEA), which is typically maintained for 2 days postoperatively. While TEA usually provides high-quality analgesia of the abdomen, drawbacks include technical difficulties with insertion, patchy or non-functioning block, pruritis and/or urinary retention due to epidural opioids, impairment of mobility due to leg weakness or the presence of a pump apparatus on an IV pole, and most importantly, associated hypotension which often results in the epidural local anesthetic infusion being discontinued. Alternatives to TEA include infiltrative blocks of the wall of the abdomen. The quadratus lumborum block (QLB) is a novel, ultrasound-guided infiltration technique whereby local anesthetic is deposited in the fascial plane between the quadratus lumborum and psoas major muscles at the level of L3-4.(1) Performed bilaterally, the QLB has been shown to provide a dermatomal block of the entire anterior abdominal wall. This may be the principal advantage of QLB over transversus abdominis plane (TAP) block, which is often patchy and restricted to a smaller area of the abdominal wall. In our institution, QLB is replacing TAP blockade for many abdominal procedures that have both upper and lower incisions or port sites. The QLB appears (both in the scant literature to date and in our institutional experience) to be reliable and technically simpler to perform than TAP blocks, as the needle is not moved once the fascial plane is breached. We wish to compare the effectiveness of QL blocks for postoperative analgesia in this population with a historical cohort that received thoracic epidural analgesia. Based on our experience, we believe that infiltrating this space with an admixture of bupivacaine and liposomal bupivacaine will result in excellent pain relief for an extended duration of time. Liposomal bupivacaine (Exparel®) is a slow-release, long-acting form of bupivacaine that has been shown to provide extended duration of analgesia and opioid sparing

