Block success and adverse events. Presence of demonstrable sensory block over 4 points on the abdomen (one in each of the 4 quadrants), as tested by response to pinprick. Subjects will be asked to report whether the stimulus feels “sharp” or “dull”, indicating block failure and success respectively. This will be done at the time of pain assessment (30 minutes after arrival to PACU, and at time points 8 hrs., 24 hrs., 36 hrs. and 48 hrs. and 72 hrs.). Subjects will be evaluated for potential adverse events related to the block including evidence of hematoma, infection, unexpected sensory or motor deficit, local anesthetic systemic toxicity, as well as transient weakness of the hip flexor muscles (a known possible side-effect of QL block).

Satisfaction with postoperative pain control. Overall subject satisfaction with pain control will be recorded on postoperative day 0 and 1 (11-point scale: 10=highly satisfied, 0=completely unsatisfied)

Hospital length of stay. Measured both by raw length of stay and by time to achieving “discharge readiness”, defined by the presence of 3 criteria: a pain score of 3 or less with ambulation, no opioids required in the preceding 6 hours, and the ability to perform self-care (go to the toilet, dress, and shower).

Incidence of opioid-related adverse events. Incidence of nausea, vomiting, ileus, constipation, orthostasis, pruritis, urinary retention, respiratory depression

Time to first mobilization. Measured from time of arrival in PACU (time zero)

Cost. Hospital costs including pharmacy-related costs, costs due to opioid-related adverse events, the cost associated with nursing interventions and drugs to treat opioid-related adverse events, and overall hospital admission costs will be calculated.

Sleep Quality. Two measures will be taken for sleep quality assessment. How much did pain interfere with falling asleep (0= no interference, 10= completely interferes). How much did pain interfere with staying asleep (0= no interference, 10= completely interferes). Measures will be taken once daily from POD 1 to POD 7 (approximately 168hrs. after surgery). If the subject is sleeping at the time assessment collection is due, the subject will not be disturbed to collect the assessments, and this will not be considered a protocol deviation.

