Historical data of 30 patients that meet inclusion criteria and meet no exclusion criteria, will be collected and for the retrospective group. The anesthesia statisticians will evaluate the following data from the patient's electronic medical record if available, including but not limited to hospital notes, anesthesia notes, medical history, medications, pain service notes, and flowsheets from admission to discharge. Electronic medical records will be used to assess the following items to compare to the prospective cohort.

Opioid consumption. Cumulative opioid consumption at 24hours, 48 hours and 72 hours. 48 hours is the primary outcome measure. Data will be drawn from PACU records and from the nursing medication records.

NRS-11. The 11-point Numeric Rating Scale (0-10) will be used as a secondary outcome measure. These will be collected from the preoperative assessment record, 30 minutes after arrival to PACU, and at time points 8 hrs., 24 hrs., 36 hrs. 48 hrs. and 72 hrs.

Thoracic epidural success and adverse events. Evidence of epidural block success/failure (as described in the anesthesia record and in daily Inpatient Pain Service notes). This will be done at the time of pain assessment (30 minutes after arrival to PACU, and at time points 8 hr, 24 hr, 36 hr and, 48 hr and 72 hr). Subject data will be collected for potential adverse events related to the epidural including evidence of hypotension, urinary retention, inability to ambulate per physical therapy. (known possible side-effect of thoracic epidural approach).

Hospital length of stay. Measured both by raw length of stay and by time to achieving "discharge readiness", defined by the presence of 3 criteria: a pain score of 3 or less with ambulation, no opioids required in the preceding 6 hours, and the ability to perform self-care (go to the toilet, dress, and shower).

Incidence of opioid-related adverse events. Incidence of nausea, vomiting, ileus, constipation, orthostasis, pruritis, urinary retention, respiratory depression

Time to first mobilization. Measured from time of arrival in PACU (time zero)

Cost. Hospital costs including pharmacy-related costs, costs due to opioid-related adverse events, the cost associated with nursing interventions and drugs to treat opioid-related adverse events, and overall hospital admission costs will be calculated.

Selection of Subjects

Criteria for inclusion in Prospective cohort:

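### Hypotension is to be collected in the epidural (TEA) cohort for comparison, but no collection is planned in the quadratus lumborum block (QLB) cohort, so the comparison lacks a QLB rate

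*Combined protocol and SAP*

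**What the plan says.** Four places in the combined protocol and SAP bear on this.

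- **Background & Significance** lists the drawbacks of TEA and ends with "most importantly, associated hypotension which often results in the epidural local anesthetic infusion being discontinued".
- **The historical-data paragraphs** introduce the retrospective items with "Electronic medical records will be used to assess the following items to compare to the prospective cohort". Under thoracic epidural success and adverse events, the items named are "evidence of hypotension, urinary retention, inability to ambulate per physical therapy".
- **Assessments, block success and adverse events** (prospective QLB cohort) asks for "potential adverse events related to the block including evidence of hematoma, infection, unexpected sensory or motor deficit, local anesthetic systemic toxicity", and adds transient hip-flexor weakness. Hypotension is not named.
- **Opioid-related adverse events** are listed in the same words for both cohorts: "Incidence of nausea, vomiting, ileus, constipation, orthostasis, pruritis, urinary retention, respiratory depression". Hypotension is not on this list either.

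The Purpose of the Study expects QLB to bring "fewer complications such as block failure, urinary retention, and pruritis". Data Analysis & Statistical Considerations plans Wilcoxon or Fisher exact comparisons of the cohorts for opioid use, pain and the other secondary outcomes.

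**The concern.** An item gathered in one cohort for the purpose of comparison should have a counterpart in the other. For hypotension it does not. The TEA charts will be searched for it; the form for QLB patients, as described, will not ask about it.

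What is at stake is how the complication results are read. A hypotension count for TEA beside an empty QLB cell invites the inference that QLB patients had none or few. Yet QLB patients also undergo general anesthesia and colectomy, so the documents give no ground for assuming a rate of zero. The apparent advantage would come from what was recorded rather than from the technique, and it would concern the drawback to which the Background gives most weight.

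**Working it through.** **1. The lists side by side.** Inputs are the Assessments section (QLB) and the historical-data paragraphs (TEA).

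| Item | TEA cohort | QLB cohort |
|---|---|---|
| Hypotension | Named, epidural-related | Not named |
| Urinary retention | Named, epidural-related and opioid-related | Named, opioid-related |
| Ambulation | Inability to ambulate per physical therapy; time to first mobilization | Time to first mobilization, same time zero |
| Orthostasis | Named, opioid-related | Named, opioid-related |
| Pruritis | Named, opioid-related | Named, opioid-related |
| Block or epidural failure | From anesthesia and pain-service notes | By pinprick |

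Of the three events in the TEA quote, urinary retention has an exact counterpart in the QLB cohort, and ambulation is largely covered by the shared mobilization outcome. Hypotension alone has none.

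**2. Whether another item fills the gap.** Orthostasis is the only haemodynamic item common to both cohorts. It sits on the opioid-related list and concerns posture. The Background is worried about hypotension that leads to an epidural infusion being stopped. One overlaps with the other, but an orthostasis rate is not a hypotension rate.

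**3. What the planned comparison can produce.** A Fisher exact test needs events and non-events in each cohort. With 30 TEA records, the TEA row can be filled. The QLB row cannot, so the risk difference is not estimable. The documents also give no definition of hypotension by threshold, duration or treatment, so even the TEA count depends on the abstractor.

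**4. The plan's own figure, and whether it is affected.** The only design calculation is for 48-hour opioid use. With a margin of 20% of 20 mg = 4 mg, SD 5.2 mg, power 0.80 and alpha 0.05 two-sided (0.025 one-sided):

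n per group = 2 × (1.960 + 0.842)² × 5.2² / 4² = 26.5, rounded up to 27, or 54 in total.

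This reproduces the stated figure. Hypotension does not enter it, so collecting hypotension leaves it unchanged.

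**5. What collecting it would buy.** The documents give no hypotension rates, so the rates below are assumptions for scale only. They show power of a two-sided Fisher exact test at 0.05.

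| Assumed TEA vs QLB rate | 27 per group | 30 per group |
|---|---|---|
| 20% vs 5% | 0.19 | 0.24 |
| 30% vs 10% | 0.31 | 0.37 |
| 30% vs 5% | 0.55 | 0.63 |
| 40% vs 10% | 0.63 | 0.71 |
| 50% vs 10% | 0.87 | 0.91 |

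Only a large difference would be detected reliably. The gain from collecting hypotension in both cohorts is an interpretable estimate with its interval, not an assured significant test.

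**The case against.** The strongest case on the other side has four parts.

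- **The QLB list is open.** It is introduced as including certain events, so hypotension could be recorded. That is true, but the TEA list is open in the same way and still names hypotension. The QLB list is limited to events related to the block, and no section plans hypotension collection in that cohort. An open list does not yield a rate.
- **Technique-specific lists are ordinary descriptive practice.** This would be a full answer if the TEA items were purely descriptive. The historical-data paragraphs say they are there for comparison.
- **Hypotension is not a named hypothesis.** This stands. The Purpose names block failure, urinary retention and pruritis, and all three are planned in both cohorts. A reader might infer from the Background that hypotension is the study's key safety contrast; the Purpose does not say so, although its list is illustrative.
- **Most of the complication comparison is sound.** This also stands. Eight opioid-related events are collected in identical words. A reader might infer that each cohort can show only the events it is searched for, or that the ambulation comparison is broken as well. The shared list contradicts the first. The shared mobilization outcome, together with discharge readiness (which involves ambulation and self-care in both cohorts), largely answers the second.

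It would also be tempting to put a number on the bias by assuming a QLB hypotension rate and counting it as zero. No section plans to code uncollected events as absent, and no rate is given, so such a figure would have no basis in the documents.

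**Conclusion.** The concern holds, limited to hypotension. As written, the plan produces a TEA rate with no QLB rate for an event that the Background calls the most important drawback of TEA and that is abstracted for comparison. The risk is one-sided: a TEA-only count can be misread only in favour of QLB.

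The magnitude cannot be derived from the documents. The conclusion rests on reading the two adverse-event lists as the data to be collected, and on there being no other plan to record hypotension in QLB patients; none appears in the documents. It does not extend to the primary outcome, the sample size, the three complications named in the Purpose, or mobilization. This is a change that should be made to a secondary safety outcome, not a flaw that undermines the study.

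**What to change.** Add hypotension to the QLB adverse-event list. Abstract it in both cohorts from the electronic record flowsheets, which the historical-data paragraphs already name as a source, using:

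- **one definition**, written down before abstraction starts;
- **one time window**, stated explicitly. TEA patients must have had the epidural started during the operation, so the investigators should decide and say whether the intraoperative period counts;
- **one source**, so that QLB patients are not assessed at the bedside for an event that TEA patients have only in the chart.

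Report the two proportions and their difference with a confidence interval, given the limited power.

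The cost is one extra abstracted field per QLB patient, with no new procedure or visit and no change to the sample size. It assumes that the QLB patients' flowsheets can be abstracted as the TEA patients' will be. If the change is not made, report the TEA hypotension rate as descriptive only, state that it was not collected in the QLB cohort, and make no between-cohort claim about it.

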Following the block, subjects will proceed to the operating room where they will undergo a standard general anesthetic with endotracheal intubation (desflurane or isoflurane in a mixture of air/oxygen). The dosing of intraoperative opioids will be left to the discretion of the attending anesthesiologist in the room.

In the Post-Anesthesia Care Unit (PACU) and on the postoperative floor, subjects will have access to oxycodone 5-15 mg PO q3h prn for rescue analgesia (the primary outcome measure). In the PACU, patients will also have access to intravenous hydromorphone if the oral opioid

provides inadequate relief. Finally, subjects may receive a standard multimodal analgesia regimen consisting of:

- Acetaminophen 975 mg PO q6h (beginning in preop holding)
- Gabapentin 600 mg PO once in holding, then 100 mg PO tid thereafter
- Ketorolac 15 mg IV prior to skin closure

While this standard regimen is expected, it may vary per clinical care team judgement and/or preference. Any alterations in this standard regimen will not be considered a protocol deviation.

Assessments

Patient assessments will be performed or recorded by a research assistant twice daily (unless otherwise specified). Assessments made after discharge will be recorded by subjects who will be provided with a diary to document the outcomes. Outcomes to be measured include:

Opioid consumption. Cumulative opioid consumption over 48 hours is the primary outcome measure. Data will be drawn from PACU records and from the nursing medication records on a twice-daily basis. Post discharge opioid use will be tracked in the take-home patient diary. The patient will be called at 7 days after surgery to collect.

NRS-11. The 11-point Numeric Rating Scale (0-10) will be used as a secondary outcome measure. Two measures will be taken with each assessment, one at rest and one with coughing. These will be conducted preoperatively, 30 minutes after arrival to PACU, and at time points 8 hrs., 24 hrs., 36 hrs. 48 hrs, 72 hrs, 96 hrs., 120 hrs., 144 hrs. and 168 hrs.

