We will use descriptive statistics (mean (SD) or frequency (%)) and group comparisons via Wilcoxon rank sum or fisher exact tests to measure differences between cohorts in opioid consumption, pain scores with rest and activity, and other secondary outcome measures.

Sample Size Justification

A difference in opioid consumption less than 20% would be considered non-inferior. Based on typical postoperative opioid consumption following laparoscopic colectomy (20mg +/- 5.2 mg), a total of 54 subjects (27 in each group) would be required to reject the null hypothesis that QL blockade is inferior in the first 48 hours with the study intervention, given an alpha of 0.05 and a power of 0.8. We plan on recruiting 45 subjects to account for dropout.

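### Time to first mobilization has no defined end event and its source can differ by cohort, so a difference in recording delay could falsely favour either QLB or TEA

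*Combined protocol and SAP*

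**What the plan says.** The Purpose of the Study section names mobilization as an expected benefit: "We believe participants who receive the quadratus lumborum block will result in improved early mobilization", by comparison with patients who had TEA.

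The outcome has the same wording in the prospective Assessments section and in the historical-data section: "Time to first mobilization. Measured from time of arrival in PACU (time zero". The start is therefore common to both cohorts. Neither section says what counts as mobilization (sitting on the edge of the bed, standing, transferring to a chair, walking) or which record supplies the stop time.

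For the QLB cohort, the general rule at the head of Assessments is: "Patient assessments will be performed or recorded by a research assistant twice daily (unless otherwise specified". Nothing more specific is given for mobilization.

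For the TEA cohort, the historical-data section says: "The anesthesia statisticians will evaluate the following data from the patient's electronic medical record if available". It then states the purpose: "Electronic medical records will be used to assess the following items to compare to the prospective cohort".

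The Data Analysis section plans "group comparisons via Wilcoxon rank sum or fisher exact tests to measure differences between cohorts". It gives no rule for missing mobilization times, no common source and no sensitivity analysis for recording delay.

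**The concern.** A time-to-event comparison needs the same stopping event read from comparable records in both groups. Here the plan allows a QLB stop time to come from study staff who visit twice a day, while a TEA stop time comes from routine charting. These sources can differ in delay and in resolution. With no defined event, they can also differ in what is being timed.

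Every QLB patient is prospective and every TEA patient is historical, so source and cohort coincide completely. If recording lags differ, the lag appears as a treatment difference, or hides one, and no test on the recorded times can tell the two apart. At stake is one of the explicit hypotheses: a positive, negative or null mobilization result would be hard to interpret.

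The plan is more careful elsewhere. For inpatient opioid use it names PACU and nursing medication records in both cohorts. For discharge readiness it lists the same three criteria in both. Mobilization has neither a common source nor a common criterion.

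**Working it through.** **The plan's own figure.** The only sample-size calculation concerns 48-hour opioid use. With a margin of 20% of 20 mg = 4 mg, SD 5.2 mg, one-sided alpha 0.025 and power 0.8:

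n = 2 × (1.96 + 0.84)² × 5.2² / 4² = 26.5, so 27 per group and 54 in total.

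This reproduces the stated figure, but it does not bear on mobilization, for which the plan gives no figure.

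**Inputs for the illustration**
- From the documents: the historical cohort, "Historical data of 30 patients that meet inclusion criteria and meet no exclusion criteria"; the stated requirement of 27 per group; and the plan to recruit 45. The Sample Size Justification does not say how the 45 divide, so three readings are shown: 45 QLB plus 30 TEA; 27 vs 27; and 45 in total including the 30 historical patients, which leaves 15 QLB.
- Assumed: SD 8 h in each cohort, no true difference, a constant delay in one cohort only, and a normal approximation at two-sided 0.05.

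**Formula.** SE = 8 × √(1/n₁ + 1/n₂). The probability of a significant result against the delayed cohort is Φ(delay/SE − 1.96). With no delay it is Φ(−1.96) = 2.5%. The formula is symmetric, so it applies whichever cohort is delayed.

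| QLB vs TEA | SE (h) | 2 h | 3 h | 4 h |
|---|---|---|---|---|
| 45 vs 30 | 8 × √(1/45 + 1/30) = 1.89 | 18% | 36% | 56% |
| 27 vs 27 | 8 × √(2/27) = 2.18 | 15% | 28% | 45% |
| 15 vs 30 | 8 × √(1/15 + 1/30) = 2.53 | 12% | 22% | 35% |

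Example, 45 vs 30 at 2 h: 2/1.89 − 1.96 = −0.90, and Φ(−0.90) = 0.18.

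**Check with the planned test.** The Wilcoxon test was simulated with 4,000 runs per scenario, lognormal times, no true difference, and a delay uniform between 0 and twice its mean. Two assumed distributions were used: mean 12 h with SD 6 h, and mean 20 h with SD 8 h. In each cell below, the first figure is for the 12 h distribution and the second for the 20 h distribution.

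| Mean delay | Falsely favoured | 27 vs 27 | 45 vs 30 |
|---|---|---|---|
| TEA 2 h | QLB | 29%, 18% | 38%, 21% |
| TEA 4 h | QLB | 75%, 49% | 88%, 63% |
| QLB 6 h | TEA | 95%, 79% | 98%, 90% |
| TEA 2 h and QLB 6 h | TEA | 68%, 47% | 80%, 57% |

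The QLB delay of 6 h is the mean lag if the stop time is taken as the next visit and visits are 12 h apart, which is one reading of twice daily. With a mean delay of 4 h in both cohorts, the two-sided error was 4.7% to 5.6%, close to nominal. What matters is the difference in delay between cohorts.

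**The case against.** The documents do not say that two instruments will be used for mobilization. The general rule lets the research assistant either make an assessment or record one, and the inpatient opioid data for QLB patients come from the same kinds of records as those for TEA patients. The assistant may copy the mobilization time from the nursing chart, and then the asymmetry shrinks or disappears. This stands as a limit: the difference in source is permitted by the plan, not required by it. It does not remove the point, because the plan does not call for a common source and the end event is undefined either way.

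A reader might infer that the design tilts the result toward QLB, on the ground that staff catch the event promptly while charts lag. The documents do not support that. They do not say that the assistant asks patients when they first got up, nor that the chart is late. If the QLB time is taken as the next scheduled visit, QLB is the delayed cohort and the bias runs toward TEA.

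It is also fair to say that no mobilization SD or delay appears in the documents, so every percentage above is conditional. Finally, this is one secondary outcome in a study that openly uses a historical comparator. The primary outcome and the sample size are unaffected.

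**Conclusion.** The concern holds as differential ascertainment of unknown direction. For a named hypothesis, the interval has a fixed start, no defined end and a source that may differ by cohort. The planned analysis cannot separate a recording difference from a recovery difference.

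Under the stated assumptions, a one-cohort delay of 2 to 4 h raises the chance of a false significant result in the corresponding direction from 2.5% to between 12% and 56%, depending on the delay and on how the 45 recruits are read. The simulated rank-sum test gives rates of similar or greater size. These figures show sensitivity to delay and do not estimate the bias in this trial. The claim that QLB will be falsely favoured goes further than the text allows. The point should be settled before mobilization times are compared.

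**What to change.** - Define one end event for both cohorts: first documented out-of-bed mobilization.
- For the comparison, take its time from the same chart flowsheet field in both cohorts. Flowsheets are already listed among the historical sources. Keep any research-assistant time in QLB as a cross-check only.
- Report the number of undocumented times by cohort. Do not give them the worst rank in the main analysis: if charting is thinner in the historical cohort, that rule would itself push the result toward QLB. Vary their handling in a sensitivity analysis.

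The cost is one definition and extraction of one flowsheet field for the QLB patients. Sample size, treatment and patient contact do not change. The downside is that charted times are less precise than observed ones. A shared field also makes equal delay more plausible without guaranteeing it, so the QLB cross-check is worth reporting.
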